### 8.3.7 ADDITIONAL EFFECTIVNESS OBJECTIVES

To assess the penile length and girth, number of pads used daily and pad weight (24-hour test).

#### Endpoint:

The endpoint is the change in each of the following measurements from baseline to 1 year post-operative follow-up.

- Inflated penile length measurement (measured from suprapubic fat pad to tip)
- Inflated penile girth measurement (circumference measured 1cm proximal to the proximal end of the corona)
- Number of pads used daily (if incontinence indicated pre-operatively)
- Pad weight (24-hour test) (if incontinence indicated pre-operatively)

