    - Total number of RTEs per cylinder (0, 1, 2, 3, 4)
    - Total length of RTEs per cylinder (specify: 0.5 to 6.5 cm)
  - AMS 700® Penile Prosthesis (3–piece inflatable)
    - InhibiZone®-impregnated (Y/N)
    - Cylinder type (CX, LGX, CXR, Ultrex, CXM)
    - Cylinder length (10, 12, 14, 15, 16, 18, 21, 24 cm)
    - Total number of RTEs per cylinder (0, 1, 2, 3, 4)
    - Total length of RTEs per cylinder (specify: 0.5 to 7.5 cm)
    - Pump type (MS Pump, Tactile pump, Inflate/Deflate)
    - Preconnect (Y/N)
    - Reservoir (Spherical 65 ml, Spherical 100 ml, Conceal 100 ml)
    - Reservoir placement (space of Retzius, Sub-muscular, Sub-Scarpa's fascia, other – specify)
    - Reservoir separate incision (Y/N)
- Drain (Y/N)
  - o If Yes, Type
- Dressing
  - None, compression/mummy wrap, noncompressive dressing
- Concurrent procedures (Y/N)
  - If Yes, specify procedure(s): ventral

phalloplasty, ligament release, circumcision, suprapubic fat pad reduction, spermatic cord/testicular procedure, AMS 800 (single or multiple incision), sling (specify sling type and single or multiple incision), other - specify

- Significant corporal fibrosis or scarring noted (Y/N)
- Curvature correction procedure(s) (e.g., for Peyronie's Disease)(Y/N)
  - If Yes: Initial intraoperative curvature measurement (angle of curvature with inflated device using a goniometer or protractor)
  - If Yes: Correction technique (Wilson/Delk remodeling, tunical incision, incision and grafting, or plication)
  - Curvature measurement after correction
  - Second correction? If Yes, same set of questions as above.
- Patient status post-op: Admitted/inpatient/≥24 hours or same day discharge/outpatient/<24 hours
  - If admitted/inpatient/≥24 hours is chosen, include: number of days in the hospital
- Length of procedure (measured from time of first incision to time of closure)
- Intra-operative penile length measurement with device inflated (measured from suprapubic fat pad to tip)
- Intra-op penile girth measurement with device inflated (circumference measured 1cm proximal to the proximal end of the corona)
- Intra-op stretched penile length measurement with device deflated (measured from suprapubic fat pad to tip)
- Foley in place at discharge? (Y/N)

Follow-up is required 1 year post-operatively. *Additional follow-ups will be determined per the physician's standard practice up to 5 years.* Follow-up data will include:

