### 4 REGISTRY DESIGN SUMMARY

The PROPPER Registry is a post-market, multi-center, non-interventional, observational collection of clinical outcomes for patients implanted with a BSC penile prosthesis for the treatment of erectile dysfunction.

As an observational collection, the registry does not dictate patient selection for implantation of BSC devices, and does not direct physicians in the medical and surgical management of patients. Physicians are free to select and manage their patients according to their usual practice. Concomitant urological procedures are allowed and will be recorded. However, outcomes data on these procedures will not be collected, with the exception of select data for any concomitantly implanted AMS 800 Artificial Urinary Sphincters or AdVance slings for the treatment of incontinence.

BSC recommends that all devices are implanted according to the device specific Instruction for Use (IFU) and/or Operating Room (OR) manuals and the site or physician's standard of care.

Patient data will be collected from the baseline/pre-operative visit, the procedure, and follow up evaluations which will occur according to each physician's standard of care, up to 5 years post-operatively. A 1=year follow up evaluation will be required, and a 2-year follow-up evaluation will be strongly encouraged. Follow-up evaluations may occur during visits with the physician and/or by telephone or mail.

Each physician will determine if the device implantation procedure was successful based on his/her standard of care. Any reported intra-operative complications will be collected in the registry database. Success will be measured post-operatively by querying patients about device use.

The PROPPER Registry is designed to obtain post market safety and effectiveness information as well as to serve as an active surveillance system for collecting device related events or complications and malfunctions in patients implanted with BSC penile prostheses and reporting product complaints to BSC. This will provide a robust database of clinical information from which a number of analyses can be performed.

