#### Statistical Analysis:

Descriptive summary statistics for penile length and girth, number of pads used daily and pad weight at baseline and 1-year follow up, and the change from baseline and 1year follow up will be calculated and summarized for each device type and overall for all BSC penile prostheses recipients. For within patient change at 1-year follow up compared to baseline, signed rank sum test or paired t-test may be used when applicable.

Additional analyses may also be used to summarize the values at the other follow up time points with data available along with changes from baseline for each device type and overall for all BSC penile prostheses recipients.

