#### Determination of Patients for Analysis:

All enrolled patients that received a BSC penile prosthesis with data available will be included.

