## 8.5 IMPLANTATION DATA

Descriptive summaries of all available implantation data collected in the registry database will be prepared, to include the number of patients (and percentage or range of values, as applicable) with recorded data within each device type and the full patient group in the following categories:

- Date of procedure (range)
- Original (virgin), revision, salvage, or replacement implant (if revision or salvage, with or without washout)
- Surgical approach (percentage of patients by category: Penoscrotal (PS), Infrapubic (IP), Subcoronal (SC) and Other)
- Implant model type
  - o Spectra™ Concealable Penile Prosthesis
    - Cylinder diameter (9.5, 12, 14 mm)
    - Cylinder length (12, 16, 20 cm)
    - Total number of RTEs per cylinder (0, 1, 2)
    - Total length of RTEs per cylinder (specify: 0.5 to 7.5 cm)
  - AMS Ambicor® Penile Prosthesis (2-piece inflatable)
    - Cylinder diameter (12.5, 14, 15.5 mm)
    - Cylinder length (14, 16, 18, 20, 22 cm)
    - Total number of RTEs per cylinder (0, 1, 2, 3, 4)
    - Total length of RTEs per cylinder (specify: 0.5 to 6.5 cm)
  - AMS 700® Penile Prosthesis (3–piece inflatable)
    - InhibiZone-impregnated
    - Cylinder type (CX, LGX, CXR, Ultrex, CXM)
    - Cylinder length (10, 12, 14, 15, 16, 18, 21, 24 cm)
    - Total number of RTEs per cylinder (0, 1, 2, 3, 4)
    - Total length of RTEs per cylinder (specify: 0.5 to 7.5 cm)
    - Pump type (MS Pump, Tactile pump, Inflate/Deflate)
    - Preconnect
    - Reservoir (Spherical 65 ml, Spherical 100 ml, Conceal 100 ml)
    - Reservoir placement (space of Retzius, Sub-muscular, Sub Scarpas's fascia, other)
    - Reservoir separate incision
- Drain (None or Type)
- Dressing (None, compression/mummy wrap, non-compressive dressing)
- Concurrent procedures (ventral phalloplasty, ligament release, circumcision, suprapubic fat pad reduction, spermatic cord/testicular procedure, AUS (including single or multiple incision), sling – (including sling type and single or multiple incision)
- Significant corporal fibrosis or scarring noted
- Peyronie's Disease

- Initial intraoperative curvature measurement (angle of curvature with inflated device using a goniometer or protractor)
- Any curvature correction procedure(s) performed (including correction technique (Wilson/Delk remodeling, tunical incision, incision and grafting, or plication)
  - Curvature measurement after correction

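### Section 8.3.7 pools penile length change across men with and without concurrent length-altering surgery, and leaves the baseline that decides whether this matters undefined

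*Combined protocol and SAP*

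**What the plan says.** All references are to the combined protocol and SAP.

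- **Endpoint (8.3.7).** "The endpoint is the change in each of the following measurements from baseline to 1 year post-operative follow-up"; the first item is "Inflated penile length measurement (measured from suprapubic fat pad to tip"). Section 8.3 introduces these outcomes as effectiveness of the prostheses.
- **Analysis (8.3.7).** Length and its change "will be calculated and summarized for each device type and overall for all BSC penile prostheses recipients". A paired t-test or signed rank test is optional. No covariate is named.
- **Analysis set (8.3.7).** "All enrolled patients that received a BSC penile prosthesis with data available will be included"
- **Concurrent surgery.** Section 4 states: "Concomitant urological procedures are allowed and will be recorded". The synopsis form list includes "ligament release, circumcision, suprapubic fat pad reduction", as well as ventral phalloplasty. Curvature correction (remodeling, tunical incision, grafting or plication) is a separate item. Section 7 makes both the concurrent-procedure and the curvature-correction fields required.
- **Use of those fields.** Section 8.5 counts them as implantation data, beginning "Concurrent procedures (ventral phalloplasty, ligament release, circumcision, suprapubic fat pad reduction". They are not carried into 8.3.7. The subgroup list in 8.4.1 does not name them, although it is expressly not exhaustive.
- **Baseline.** The synopsis and 8.4.3 list only flaccid and stretched lengths as pre-operative data. Inflated length first appears among the intra-operative items (synopsis, 8.5). Table 1 merges baseline and procedure into one column and marks penile measurements optional throughout.

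**The concern.** A change in length measured from the fat pad can come from the device, from other surgery on the penis, or from surgery on the fat pad itself. The plan foresees all three in one operation and summarises them as one figure under prosthesis effectiveness. The synopsis and section 4 also say that outcomes of concomitant procedures are not collected, except for the artificial sphincter and the male sling. The length effect of the other procedures would then appear only inside the prosthesis result.

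At stake is the interpretation of the mean length change, overall and by device type. Its value could depend on the mix of concurrent surgery among the men who happened to be measured. The same holds for the Peyronie's disease subgroup named in 8.4.1, where curvature correction is to be expected.

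**Working it through.** The plan gives no target, SD, alpha or sample size for penile length, so there is no planned figure to reproduce. The check is a reading of the text followed by a scaling exercise.

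**Step 1: which procedures touch the measurement.** Fat pad reduction alters the point from which length is measured. Ligament release, ventral phalloplasty and curvature correction act on the penis and leave that landmark alone. Girth is taken 1 cm proximal to the corona, so the landmark argument does not reach it.

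**Step 2: which baseline.** Section 8.3.7 does not name one.
- If baseline is pre-operative, as the labels in the synopsis and 8.4.3 suggest, concurrent surgery lies between the two measurements and its effect is inside the change.
- If baseline is the intra-operative inflated length, the only like-for-like value, the answer depends on order. Taken after the concurrent procedure, it already contains the immediate effect, which then largely cancels. Taken before, it does not.
- The plan does not state the order. It also does not say whether the fat pad is compressed when measuring; compression would shrink the fat-pad part.

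**Step 3: size.** Let p be the share of measured men with such a procedure, s the mean shift in measured length it causes, and c the fraction of that shift already present in the baseline value.

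Shift in the pooled mean change = p x s x (1 - c)

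None of p, s or c is in the documents. With c = 0 (pre-operative baseline) and assumed p and s:

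| p | s (cm) | shift (cm) |
|---|---|---|
| 2% | 0.5 | 0.02 x 0.5 = 0.01 |
| 5% | 1 | 0.05 x 1 = 0.05 |
| 10% | 1 | 0.10 x 1 = 0.10 |
| 20% | 2 | 0.20 x 2 = 0.40 |

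With c = 1 every entry is zero.

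**Step 4: small strata.** Section 8.1 expects 15 Ambicor and 20 Spectra implants per enrollment year. One man with an assumed 1 cm shift moves the mean by 1/15 = 0.067 cm or 1/20 = 0.05 cm. Two such men move it by 0.133 cm or 0.10 cm. Because measurement is optional, the measured strata may be smaller and the effect of one man larger.

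**Step 5: the optional paired test.** Assume a two-sided 0.05 level, 500 measured men, no true device change, c = 0, and a within-group SD of change of 1 or 2 cm. The SD of the pooled change is sqrt(SD² + p(1 - p)s²), and a normal approximation gives the rejection rate.

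| p, s | SD 1 cm | SD 2 cm |
|---|---|---|
| 2%, 0.5 cm | 5.6% | 5.1% |
| 5%, 1 cm | 19% | 9% |
| 10%, 1 cm | 57% | 20% |

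For the second row with SD 1: sqrt(1 + 0.0475) = 1.023; standard error 1.023/sqrt(500) = 0.0458; 0.05/0.0458 = 1.09; rejection rate 19%. The test stays close to its nominal level when the procedures are rare and departs from it clearly when they are not.

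**The case against.** The strongest reply concerns the baseline. The endpoint is inflated length, and inflated length does not exist before the device is in. If the intra-operative value is the baseline and follows the concurrent surgery, most of the supposed bias disappears. This stands, and it makes the point conditional. It does not remove it, because the plan nowhere says that this value is the baseline or when it is taken, and its own labels point to pre-operative lengths.

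A reader might infer that the registry will report a landmark artefact as a device gain. The documents do not support that. They give neither the frequency nor the effect of these procedures, and effects in opposite directions could offset each other. Only fat pad reduction touches the landmark, so it would also be wrong to say that ligament release moves the reference point. Nor is a formal comparison of device types at risk: 8.3.7 plans by-device summaries and within-patient tests only.

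It is also fair to say that 8.4.1 leaves room for a subgroup by concurrent procedure. But that list is permissive; it does not commit anyone to the split.

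Finally, one can argue that a real-world registry (section 3.1) should show everyone, and that removing curvature-corrected men from the main summary would discard many men with Peyronie's disease. This is a good reason to keep the all-patient summary. It is no reason against showing the groups side by side.

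**Conclusion.** The point holds in conditional form. Length change is pooled across men with and without concurrent surgery that can alter measured length, is presented as prosthesis effectiveness, and has no stated baseline that would settle whether the surgery falls inside the change.

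The size is unknown. On an assumed 2-20% of men and 0.5-2 cm per man, with a baseline that precedes the surgery, it is 0.01-0.40 cm. That is negligible at the lower end and material at the upper end or where a stratum holds 15 to 20 men. With an intra-operative baseline taken after the surgery it would be much smaller. The point concerns length; nothing here calls for restricting girth.

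Severity is minor. Penile measurements are optional at every visit, the endpoint is an additional descriptive one, any test is optional, and no sample size or decision rests on it.

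**What to change.** In 8.3.7:

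1. State that the baseline for inflated length is the intra-operative inflated measurement, and record whether it was taken before or after any concurrent procedure.
2. Keep the all-patient summary by device type and overall.
3. Add length change in separate rows: men with none of the four procedures; men with fat pad reduction, ligament release or ventral phalloplasty but no curvature correction; and men with curvature correction, with or without the others.
4. Base any statement about the prosthesis effect on length on the men with none of them.
5. Leave the girth summary as it is.

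**Cost.** The procedure fields are already required, so the split needs only SAP wording and a few table rows. The order of measurement is one new form item and may not be recoverable for men already implanted; they should be shown as order unknown. Fewer men will stand behind the prosthesis-only statement. Because the device is already in place at the intra-operative measurement, the endpoint then describes change in inflated length since implantation, not gain over the pre-operative state, and the report should say so.

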#### Statistical Analysis:

Descriptive summary statistics for penile length and girth, number of pads used daily and pad weight at baseline and 1-year follow up, and the change from baseline and 1year follow up will be calculated and summarized for each device type and overall for all BSC penile prostheses recipients. For within patient change at 1-year follow up compared to baseline, signed rank sum test or paired t-test may be used when applicable.

Additional analyses may also be used to summarize the values at the other follow up time points with data available along with changes from baseline for each device type and overall for all BSC penile prostheses recipients.

#### Determination of Patients for Analysis:

All enrolled patients that received a BSC penile prosthesis with data available will be included.

### 8.4 ADDITIONAL DATA ANALYSIS

### 8.4.1 SUBGROUP ANALYSIS

Subgroups of patients for which analyses of safety and effectiveness outcomes may be performed based on relevant available data include, but are not limited to, the following:

- Implant type and model (AMS 700®, Ambicor®, Spectra™)
  - AMS 700® LGX
  - AMS 700® Series with Conceal
  - AMS 700® MS Pump
  - AMS 700® with InhibiZone
- Original (virgin) and revision implants (if revision with or without washout)
- Primary etiology of ED (e.g., Diabetes, Cardiovascular disease, Radical prostatectomy, Peyronie's disease)

### 8.4.2 PHYSICIAN DATA

Recorded data from each practice will be summarized in the following categories:

- Practice type (private or academic)
- Main setting for procedures (Hospital or ASC)
- Standard device cycling instructions to patients receiving IPPs (number and percentage) a description of each physician's recorded device cycling protocol will also be prepared.

### 8.4.3 BASELINE/ PRE-OPERATIVE DATA

The following demographic and patient characteristics will be summarized (including mean, median, and standard deviations) for patient groups based on the type of BSC device implanted and overall for all BSC penile prostheses recipients:

- Age
- Duration of ED (years or months)
- Pre-op flaccid penile length (measured from suprapubic fat pad to tip)
- Pre-op stretched penile length (measure from suprapubic fat pad to tip)
- Pre-op flaccid girth (circumference measured 1cm proximal to the proximal end of the corona)
- Number of office visits in past year for treatment of depression
- Duration (weeks) and Frequency (times/day) of VED use prescribed preoperatively
- Number of pads used daily (for SUI)
- Pad weight (24-hour test) (for SUI)
- Urodynamics (for SUI): Post-void residual (PVR) volume (ml), maximum flow rate (ml/sec)

The number and percentage of patients with recorded baseline data will also be summarized within each device type and the full patient group in the following categories:

- Race/Ethnicity
- Primary etiology of ED
  - o Organic
    - Diabetes
    - Cardiovascular disease
    - Neurologic disorder
    - Peyronie's disease
    - Other organic (specify)
  - $\circ$  Acute
    - Radical prostatectomy (RP) (robotic, open or laparoscopic)
    - Radical pelvic surgery (other than RP)
    - Pelvic radiation therapy
    - Pelvic trauma or injury
    - Spinal cord injury
    - Venous Leak
    - Priapism
    - Other acute (specify)
- Concomitant medical conditions and concomitant medications:
  - o premature or rapid ejaculation/PE
  - o climacturia
  - o cardiovascular disease
  - o diabetes
  - Peyronie's disease
  - $\circ$  steroid use
  - o anticoagulant use
  - o anti-depressant use
  - Venous Leak
  - o stress urinary incontinence/SUI
    - Etiology of incontinence (radical prostatectomy, pelvic irradiation, and other)
    - Previous treatment(s) for incontinence (behavior modification, pelvic floor muscle training, transobturator male sling, artificial urinary sphincter/AUS, and other)
    - Cystoscopy findings (bladder neck contracture, other) (for SUI)
    - Any detrusor overactivity (DO) or detruser sphincter dyssynergia (DSD) (for SUI)
  - any others recorded
- Previous treatments used for ED (PDE-5 inhibitor, VED, ICI, combination therapies, previous/failed penile implants)
- Patients with any office visits in past year for treatment of depression

- Patients taking any depression medication in past year
- Patients with VED and/or penile traction therapy prescribed pre-operatively

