- Relevant concomitant medical conditions and concomitant medications that might impact ED (premature or rapid ejaculation/PE, climacturia, cardiovascular disease, diabetes, Peyronie's disease, stress urinary incontinence/SUI, steroid use, anticoagulant use, anti-depressant use, venous leak, and Other, please specify) – with the following sub-

assessments if SUI checked:

- Etiology of incontinence (radical prostatectomy, pelvic irradiation, and other – please specify)
- Previous treatment(s) for incontinence (behavior modification, pelvic floor muscle training, transobturator male sling - specify model and implant date, artificial urinary sphincter/AUS – specify implant model date, other - specify)
- Number of pads used daily
- Pad weight (24-hour test)
- Urodynamics: Post-void residual (PVR) volume (ml), maximum flow rate (ml/sec), any detrusor overactivity (DO) or detruser sphincter dyssynergia (DSD)
- Cystoscopy findings (bladder neck contracture, other – specify)
- Pre-op flaccid penile length (measured from suprapubic fat pad to tip)
- Pre-op stretched penile length (measure from suprapubic fat pad to tip)
- Pre-op flaccid girth (circumference measured 1cm proximal to the proximal end of the corona)
- Duration of ED (years or months)
- Previous ED Treatments [ PDE-5 inhibitors (PDE-5s), vacuum erection device (VED), intracavernosal injection (ICI), Combination therapies, previous/failed penile implants), other, specify]
- Patient query any office visits in past year for treatment of depression Y/N
  - If Yes: approximately how many visits
  - If Yes: taking any depression medication
- Was VED and/or penile traction therapy prescribed pre-operatively? (Y/N)
  - If Yes: specify Duration (weeks) and Frequency (times/day)
- Baseline effectiveness/quality of life assessments

Implantation surgery data will include:

- Date of procedure
- Original (virgin), revision, salvage or replacement implant
  - If revision or salvage, washout (Y/N)

- Surgical approach (Penoscrotal (PS), Infrapubic (IP), Subcoronal (SC) or "Other, please specify")
- Implant model type:
  - Spectra™ Concealable Penile Prosthesis
    - Cylinder diameter (9.5, 12, 14 mm)
    - Cylinder length (12, 16, 20 cm)
    - Total number of RTEs per cylinder (0, 1, 2)
    - Total length of RTEs per cylinder (specify: 0.5 to 7.5 cm)
  - AMS Ambicor® Penile Prosthesis (2-piece inflatable)
    - Cylinder diameter (12.5, 14, 15.5 mm)
    - Cylinder length (14, 16, 18, 20, 22 cm)

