### 7 DATA COLLECTION

Data will be collected via internet-based electronic data capture (EDC) with paper based questionnaires for collection of patient-reported outcomes (PRO) data. The PRO data will be entered into the registry database by the physician, physician staff or BSC staff. The EDC module will be developed and maintained by BSC.

Physicians are not required to complete all data fields in the database. Each will be asked to enter the required data at baseline/procedure and one-year follow-up for each

patient and optional data based on the information that they collect per their own standard of care.

Additional outcomes will be collected at whatever time frames are deemed appropriate by the physician, based on their standard of care for treatment of ED.

This is an observational collection of prospective patient data, with the following data required for each enrolled physician and patient:

- basic practice information for each physician
- baseline/pre-operative patient information: age, race/ethnicity, primary etiology of ED, relevant concomitant medical conditions and concomitant medications that might impact ED
- implantation surgery data: date of procedure, surgical approach, implant model type, drain, dressing, concurrent procedures, significant corporal fibrosis or scarring noted, curvature correction procedure(s) (e.g., for Peyronie's disease), and patient status post-op
- 1-year post-operative follow-up (at a minimum): each patient is asked 3 standardized questions during a visit or by phone to record any potential device related complications and their outcomes, patient satisfaction with implanted device(s) and use of device.

Refer to Table 1 for the study data collection schedule.

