### 7.2 DEPRESSION HISTORY QUESTIONS

The following patient questions used to assess depression will be optional at baseline and at each annual follow-up.

- Have you had any office visits in past year for treatment of depression? (Y/N)
  - If Yes: Approximately how many visits?
  - If Yes: Are you taking any medication for treatment of depression?
     If Yes: How many months have you taken the medication?

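### The planned baseline row on past-year depression medication rests on a question about current use, asked only of men with a depression office visit, and its denominator is not stated

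*Combined protocol and SAP*

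**What the plan says.** The plan touches depression medication in four places.

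- **Section 8.4.3 (baseline summaries)** lists a row for men with a depression office visit in the past year and, directly after it, "Patients taking any depression medication in past year". Numbers and percentages are given by device type and overall, for patients with recorded baseline data. No denominator is set for this row.
- **Section 7.2 (the question wording)** first asks, Yes or No, about office visits for depression in the past year. Under a Yes come the number of visits and "If Yes: Are you taking any medication for treatment of depression". Under a further Yes comes "If Yes: How many months have you taken the medication". The whole set is optional: "The following patient questions used to assess depression will be optional at baseline and at each annual follow-up".
- **The synopsis** nests the medication item in the same way at baseline and at follow-up: "If Yes: taking any depression medication". It puts no time window on the medication. The notes under Table 1, however, describe the depression history entry as covering any depression treatment over the preceding year.
- **The concomitant conditions and medications list** in the synopsis includes "steroid use, anticoagulant use, anti-depressant use, venous leak, and Other, please specify". This item does not depend on the visit question. Section 7 places "relevant concomitant medical conditions and concomitant medications that might impact ED" among the data required for each patient, and section 8.4.3 gives anti-depressant use its own row.

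**The concern.** The label and the question differ in two ways. The label covers any use in the past year, while the question covers use now. The label carries no restriction on who is counted, while the question reaches only men with an office visit for depression. No other question asks about depression medication at any time in the past year, so the row cannot be filled as labelled.

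What is at stake is how a published baseline table is read. The protocol's background names depression as associated with erectile dysfunction, and the row will appear for each device type. A reader would take it as the prevalence of past-year treatment, which it is not. The same table will also carry an anti-depressant use figure of different scope, with nothing to explain why the two differ.

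**Working it through.** The documents state no figure to reproduce, so the check is a comparison of wording followed by an illustration on assumed values.

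**Step 1. Who is recorded.** Section 7.2 records a man as a medication user only if he had a depression visit in the past year and is taking medication when asked. Reporting error aside, every such man is a past-year user, so the recorded count cannot exceed the true count. It omits:

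- users with no depression office visit in the year;
- men who took medication in the year and stopped before baseline.

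The months-of-use question does not recover the second group, because it follows only a Yes to current use.

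**Step 2. Count.** Let N be the men answering, p the true share with past-year use, g the share of users with at least one depression visit, and c the share of those still taking medication at baseline. Then

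recorded count = N × p × g × c, and the share of true users captured = g × c.

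All four values are assumptions. With N = 500:

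| p | g | c | true users | recorded | captured (g × c) | recorded / N |
|---|---|---|---|---|---|---|
| 20% | 0.9 | 0.9 | 100 | 81 | 81% | 16.2% |
| 20% | 0.7 | 0.9 | 100 | 63 | 63% | 12.6% |
| 20% | 0.5 | 0.7 | 100 | 35 | 35% | 7.0% |
| 10% | 0.9 | 0.9 | 50 | 40.5 | 81% | 8.1% |
| 10% | 0.7 | 0.9 | 50 | 31.5 | 63% | 6.3% |
| 10% | 0.5 | 0.7 | 50 | 17.5 | 35% | 3.5% |

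For example, 500 × 0.20 × 0.7 × 0.9 = 63. Capture is complete only if g = c = 1.

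**Step 3. Percentage.** The last column counts every man who was not asked as No, and it is too low throughout. Now suppose that only men who were asked form the denominator. Let w be the share of non-users with a depression visit. Then

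men asked = N × [p × g + (1 − p) × w].

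- p = 20%, g = 0.7, c = 0.9, w = 5%: asked = 500 × (0.14 + 0.04) = 90; 63/90 = 70%, against a true 20%.
- p = 10%, g = 0.5, c = 0.7, w = 5%: asked = 500 × (0.05 + 0.045) = 47.5; 17.5/47.5 = 36.8%, against a true 10%.
- p = 20%, g = 0.9, c = 0.9, w = 10%: asked = 500 × (0.18 + 0.08) = 130; 81/130 = 62.3%, against a true 20%.

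In general this percentage is p × g × c / v, where v is the share of all men with a visit. It exceeds p whenever g × c is larger than v. In the three examples g × c is 63%, 35% and 81%, against v of 18%, 9.5% and 26%.

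**Result.** The count is too low unless g = c = 1. The percentage can err in either direction, depending on a denominator that section 8.4.3 leaves open.

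**The case against.** Four arguments can be made for the plan.

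1. **The denominator.** A reader might infer that men who were not asked are scored as untreated, so that the percentage must be too low. The documents do not support this. Section 8.4.3 refers to patients with recorded baseline data and does not say whether a man never asked counts as No or as not recorded. The argument stands against a firm claim that the percentage is understated. It leaves the undercount of patients untouched and adds an unstated denominator to the problem.
2. **The anti-depressant use item.** It does not depend on the visit question and belongs to the required data, so a man on repeat prescriptions without a visit can appear there. This is real but partial mitigation. The item has no past-year window, so men who stopped are not reliably recovered. A reader might also take a difference between the two rows as an error in itself. It is not, because items of different scope need not agree.
3. **The intended window.** The Table 1 notes speak of treatment over the past year, and the synopsis item sits under a past-year question without an explicit present tense. The row label may therefore express the intent and the wording in section 7.2 may be the slip. This is plausible and bears on which end to correct. It does not remove the mismatch, since section 7.2 gives the explicit question wording.
4. **The source of the row.** Section 8.4.3 does not name the field. That is true, but the nested item is the only one worded as depression medication, and anti-depressant use already has its own row.

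**Conclusion.** The row is wrong as written: its label claims a past-year window and carries no visit restriction, and the question behind it supplies neither. This rests on the nested item in section 7.2 being the source, which is the evident reading.

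The undercount holds for the number of patients. For the percentage, only the lack of a defined denominator is established. The size cannot be derived from the documents. The 35% to 81% capture above follows from the assumed values and is not an estimate, and because the questions are optional, missing answers add further uncertainty.

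Importance is low. A reader might infer that study conclusions are affected, but depression is not among the safety or effectiveness endpoints or the listed subgroups. The row is a descriptive baseline line that enters no planned test and has no bearing on sample size.

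**What to change.** Either of two changes is enough.

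- **Change the question.** Ask every man whether he took medication for depression at any time in the past year, independently of the visit question, and keep current use and months of use as follow-on items. This matches the intent in the Table 1 notes and lets the row keep its label. It costs one un-nested question in section 7.2, the synopsis and the data form. The question recurs at annual follow-up, so the change should be made there too. Answers to the old and new wording should not be pooled.
- **Change the label.** For data already collected, call the row current depression medication among men with a past-year office visit for depression, and use the men with a visit who answered the medication item as the denominator. This costs one table label.

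In both cases, state how men who were not asked and men who left the optional questions blank are handled. Present the row next to anti-depressant use, with a footnote on how the two items differ.
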